1) **Protocol Title:** Combining Lovastatin and a Parent-Implemented Language Intervention in a Multi-Modal Treatment of Fragile X Syndrome

2) Autl	nor of Protocol
XUC	C Davis Researcher
□ Re	searcher from other institution
□ Pr	ivate Sponsor
	operative Group
□ Ot	-

3) Objectives

Aim 1. Test the efficacy of a 20 week multi-modal treatment comprised of lovastatin and the Parent-implemented Language Intervention (PILI) for children with FXS. Children will be randomized to drug or placebo in a double-blind design with all participating in the PILI. The primary endpoint will be a spoken language composite and the secondary endpoint will be challenging behavior. We will test the following hypotheses:

Hypothesis 1a. Improvements in spoken language and behavior will be greater among lovastatin-treated than placebo treated participants.

Hypothesis 1b. Improvements in parental use of the PILI-targeted strategies will be associated with greater improvements in child language and behavior, especially in the lovastatin-treated group, thereby demonstrating benefit of the combined intervention.

Aim 2. (a) Identify biomarkers in peripheral immune cells associated with FXS and the efficacy of treatment and (b) elucidate the cellular/molecular mechanisms by which lovastatin influences MEK/ERK and Rho GTPase signaling pathways and immunological abnormalities associated with FXS.

Hypothesis 2a. Lovastatin corrects core biochemical and physiological impairments by normalizing Ca2+dependent and/or Ca2+-independent regulation of the MEK/ERK signaling pathway.

Hypothesis 2b. Lovastatin normalization of MEK/ERK signaling and/or Rho GTPase signaling is mediated by its effects on isoprenoid synthesis.

Hypothesis 2c. Individuals with elevated inflammatory cytokines will be more responsive to lovastatin.

4) Background

This is the first multi-modal treatment to combine a targeted treatment for FXS, lovastatin, with an innovative parent-implemented intervention (PILI) targeting language and challenging behavior delivered through telehealth technology. Our hypothesis is that targeted treatments will be more effective when applied in combination with PILI. We also will examine whether changes in the activity of key

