Once eligibility is confirmed, subjects will be approached to obtain their authorization to access and use their health information for the research. Please see Section 14 for additional information regarding Data Management and Confidentiality.

8) Compensation to the Subjects

Subjects will not be compensated for their participation. Possible expenses to the subject's family include time spent at the clinic as well as expenses for travelling. Therefore subjects who would otherwise not be able to participate may be eligible for travel reimbursement for travel costs incurred as specified in question 25.

9) Study Timelines

We anticipate seeing 30 pilot participants in the first 18 months under consent form C. During this same time period up to an additional thirty participants and their mothers will be seen under consent form A, phases 1 and 2 of the study. During Phase 3, 50 participants and their parent/caregiver will be recruited into the clinical trial portion utilizing consent form B. In addition, 3 subjects will be recruited into phase 4, under consent form D. Phases 2,3, and 4 of the study, using consent forms A, B and D, will occur over the last 3.5 years of the project).

10) Study Endpoints

The primary outcome measure is a spoken language composite measured at baseline and at the end of treatment. Comparison of the two treatment groups on the outcome measure will be made through analysis of covariance, adjusted for baseline values on that measure using an intent-to-treat approach. Two-sided tests will be used with alpha at .05. With this sample size, power to detect a moderate effect size of 0.6 will be 80%, assuming equal standard deviations in the groups. The assumptions we are making to estimate power are conservative as evidenced by recent published tests of a parent mediated intervention for autism (Rogers et al., 2012) and a randomized controlled trial of a drug in FXS (Berry-Kravis et al., 2012), with samples sizes of 98 and 60, respectively, and behavioral outcome measures.

Analysis of our secondary outcome measure, the social avoidance subscale of the FXS- normed ABC, as well as the exploratory VAS and CGI will follow the same approach as the primary analysis. Additional analyses will examine potential child moderators of response to lovastatin (age, Leiter, ADOS symptom severity) using linear regression.

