Aim 1. Hypothesis 1b. We will use linear regression to test the relationships between parent behaviors and child outcome at 20 weeks (i.e., spoken language composite). The regression will include main effect terms for both treatment and parent behavior as well as the interaction term, while controlling for baseline values of the parent and child measures. Various parent confounders will be

evaluated as well (e.g., SCL-90-R severity score). The main effect of the parent behavior will test the contribution of PILI, whereas the interaction term will test the value of the combined treatment. These analyses will be done separately with two parent behavior measures (parent verbal responsiveness composite and quality of caregiver involvement score).

Analyses will be repeated for secondary outcome measures.

Aim 2. In the addressing hypotheses 2a, b, and c, we will identify biomarkers associated with FXS using a regression model for marker expression with grouping of phenotype (i.e., disease state or respond to treatment) as a predictor with important clinical cofounders as covariates. The marker performance will be evaluated using receiver operating characteristic (ROC) curves to test which biomarkers are statistically better diagnostic and prognostic tests for FXS. We will further develop predictive signatures of elements involved in MEK/ERK and Rho GTPase signaling pathways in response to lovastatin using PAM, or other pattern recognized methods. The potential biomarkers are phosphorylation of S6K1, AKt, EIF4E, and ERK/MEK as well as levels of IL-1, IL-6, IL- 10, MCP-1, IL-1alpha, IL-1beta, MMP-9, and MIF.

Based on the findings of [name] et al. (2016, American Journal on Intellectual and Developmental Disabilities) statistical power for this study is expected to be sufficient with a subject enrollment of 50. In the [name] study, a treatment effect was demonstrated with the same outcome measure and same age range in a sample size of 10 per group. In this multimodal study, it is expected that the effect of the drug, if it is to be clinically meaningful, will be at last as large as the effect of the language intervention by itself in the 2016 study. In fact, the expectation is to see expect synergistic effects with the language intervention amplifying the effect of the drug.

11) Procedures Involved

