Parent use of targeted intervention strategies and child spoken language will be assessed during joint book reading within two contexts at both the pre- and post-treatment assessment. The contexts will be 1) at the clinic visit, and 2) in the family home via distance teleconferencing. The parent/caregiver and child will look at a wordless picture book together and the parent/caregiver will be instructed to look at each page of the book and tell the story with his/her child as he/she usually would. A set of two wordless picture books will be used in each sampling context and the books will be randomly assigned to participants and counterbalanced at the pre- and post-assessment time points. The following parent and child variables will be obtained from each context and average to create composite variables. Parent variables: story-related talking, open-ended questions, use of expansions, use of intonation prompts. Child variables include: Mean length of utterances, number of different words, story-related talking, intelligibility, mazes, off-topic utterances, and repetitive utterances. Each sample will last approximately 15 minutes.

i. Parent/Child Narrative Task 1(Clinic): ICF A and B

The parent/caregiver will tell a story with the child using the wordless picture books *Frog Where are You* (version A) or *One Frog Too Many* (version B). The parent/caregiver will be encouraged to look through/familiarize themselves with the book in advance of the language sampling session (15).

min, Pre/Post Consent Form Versions A and B).

ii. Parent/Child Narrative Task 2 (Home): ICF A, B, and D

Parent/caregiver will tell a story from a wordless picture book from a selection of books that will not be used during the intervention. The parent/caregiver will be encouraged to look through/familiarize themselves with the book in advance of the language sampling session.).

iii. Parent/child structured interaction - Child: ICF D

The parent will interact with the child during four activities: joint book reading, preparation of a snack, completion of a goal-directed construction activity, and free play. The mother will be instructed to participate and involve the child as much as possible. Sessions will be coded to determine maternal use of responsive verbal interaction strategies, child spontaneous and prompted communication acts, and child challenging behaviors (20 min).

The following are exploratory measures:

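### Hypothesis 1b concerns improvement in parent strategy use, but the planned arm-by-parent-behavior interaction reads as one with the Week 20 level, which mixes starting style with improvement

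*Combined protocol and SAP*

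**What the plan says.** Section 3, Objectives, gives the hypothesis: "Improvements in parental use of the PILI-targeted strategies will be associated with greater improvements in child language and behavior, especially in the lovastatin-treated group". The quantity of interest is the parent's improvement.

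Section 10, Study Endpoints, gives the analysis. Linear regression will "test the relationships between parent behaviors and child outcome at 20 weeks". On the terms: "The regression will include main effect terms for both treatment and parent behavior as well as the interaction term, while controlling for baseline values" (for parent and child alike). The two coefficients are given separate jobs: "The main effect of the parent behavior will test the contribution of PILI", and "the interaction term will test the value of the combined treatment". The model is run separately for two parent measures and repeated for the secondary outcomes.

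Section 11(a), Parent-Child Assessment Measures, has parent strategy use measured "within two contexts at both the pre- and post-treatment assessment", so both a level and a change are available. No interaction of arm with baseline parent behavior is listed. No power, slope or parent pre-post correlation is given for this analysis.

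**The concern.** Putting the baseline parent measure in the model as a main effect turns the parent slope into a slope for improvement. It does nothing of the kind for the interaction. If the interaction is arm by Week 20 level, a difference in drug response by the way parents already talked before coaching enters the same coefficient as a difference by how much they improved.

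Section 10 assigns to that coefficient the test of the combined treatment. A positive result could therefore be reported as drug and coaching reinforcing each other when coaching-induced change played no part. Conversely, a real dependence on improvement is diluted and can be missed.

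**Working it through.** **Inputs from the documents.** Up to 50 children in the trial phase (Section 6), half on lovastatin (Section 17), so 25 per arm. "Two-sided tests will be used with alpha at .05" (Section 10).

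**Assumptions, because the documents give no values.** Child baseline to Week 20 correlation 0.67; parent baseline to Week 20 correlation *r* from 0.4 to 0.8; equal parent SDs at both times unless stated; no dropout.

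**The plan's own power figure.** There is none for Hypothesis 1b. The only one, for the primary comparison, is "power to detect a moderate effect size of 0.6 will be 80%, assuming equal standard deviations in the groups". Without baseline adjustment, 25 per arm gives z = 0.6 × √(25/2) − 1.96 = 2.121 − 1.96 = 0.161, or 56% power. Adjustment divides 2.121 by √(1 − ρ²), where ρ is the child baseline correlation; 80% then needs ρ of about 0.65 to 0.66. At ρ = 0.67, 2.121/0.742 − 1.96 = 0.90, or about 81%. The assumed 0.67 is thus close to what the plan's figure would imply. Whether that figure is justified is a separate matter.

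**Algebra.** Let P0 and P20 be the parent's baseline and Week 20 values. Since P20 = P0 + change,

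arm × P20 = arm × P0 + arm × change, with one common coefficient.

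Suppose the drug effect truly varies by γ per unit of P0 and by b per unit of change. Under randomization, with the same parent distribution in both arms, the planned interaction estimates

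γ·k + b·(1 − k), where k = r × SD(P0)/SD(P20).

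- Starting style only, γ = 0.5, r = 0.8: 0.5 × 0.8 = 0.40, although improvement has no role.
- Improvement only, b = 0.6, r = 0.5: 0.6 × 0.5 = 0.30, half the true value. At r = 0.8: 0.6 × 0.2 = 0.12.
- If the Week 20 SD is twice the baseline SD and r = 0.5: k = 0.25, so three quarters of b comes through.

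With arm × P0 also in the model, the arm × change coefficient estimates b.

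**Simulation**, n = 50, 3,000 runs per cell, average drug effect 0.3 SD. Slopes are in child SD per SD of parent behavior. Entries are rejection rates.

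| Truth | r | Planned: arm × P20 | With arm × P0 added |
|---|---|---|---|
| No moderation | 0.4–0.8 | 4–6% | 5–6% |
| Starting style, γ = 0.3 | 0.4 / 0.6 / 0.8 | 9 / 13 / 17% | 6 / 5 / 4% |
| Starting style, γ = 0.5 | 0.4 / 0.6 / 0.8 | 13 / 27 / 40% | 5 / 5 / 5% |
| Improvement, b = 0.4 | 0.5 | 13% | 31% |
| Improvement, b = 0.6 | 0.5 | 25% | 61% |
| Improvement, b = 0.6 | 0.8 | 9% | 34% |

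Repeat runs moved single cells by up to about 3 points. They put the top of the starting-style range at 42%, and the two improvement cells at r = 0.5 at 14% to 23% as planned and 33% to 60% with the added term.

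**Sensitivity to spread.** In a second simulation (child slope 0.6, residual SD 0.8, moderation 0.5 SD per SD of change), a Week 20 SD of 1.5 to 2 times the baseline SD gave 32% to 42% as planned, against 46% to 52% with the added term.

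**Arm × change alone.** In that second set-up with equal SDs, arm × change without arm × P0 rejected in 8% to 21% of trials under starting-style moderation of 0.5. Relabeling the term as change is therefore not sufficient.

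**The case against.** **The text does not say Week 20 level.** True. The words about 20 weeks may attach only to the child outcome, and change may have been intended. The level is the natural reading, because adjusting for the baseline value is what one does with a follow-up value, but it remains an inference. If change was meant, the section should say so, and arm by baseline is still missing.

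**A reader might infer that the planned test has an inflated error rate.** It does not in general: with no moderation it rejects about 5%. The excess requires real moderation by starting style. The 40% cell is demanding: with an average drug effect of 0.3 and γ = 0.5, the effect runs from −0.2 to +0.8 SD for parents one SD below and above the mean. At γ = 0.3 the range is 9% to 17%.

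**A reader might blame the low power wholly on the specification.** The sample size shares the blame: the model with both terms reaches only 31% to 61% in the equal-spread cells above. The gap also narrows if coaching widens the spread of parent behavior.

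**Level may be the right moderator.** If drug benefit depends on the language input the child actually receives, the planned term is the better one. At r = 0.8, with level moderation of 0.4 and 0.6, adding the term lowers power from 42% to 19% and from 74% to 33%. This is a genuine cost. It does not settle the choice, because the hypothesis names improvement.

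**A reader might infer that the parent main effect tests the slope in one arm only.** That would follow from 0/1 arm coding with an interaction present, but no coding is stated, and main effect can equally mean the average over arms. Without interaction terms, P20 adjusted for P0 has the same coefficient as change adjusted for P0. This is a request for clarification, not a fault shown.

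**Conclusion.** The concern holds on the natural reading of Section 10. The planned interaction does not isolate the dependence on improvement that Hypothesis 1b states, and the baseline main effect does not repair this. The algebra needs only that reading; the sizes need the assumed correlations and slopes.

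Under those assumptions, starting-style moderation alone gives a significant interaction in about 9% to 42% of trials, against about 5% with the added term. For true moderation by improvement at a parent correlation of 0.5 and equal SDs, power is about 14% to 23% as planned and 33% to 60% with the added term, still below 80%.

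A reader might take this as a threat to the trial's main result. The documents do not support that: the primary randomized comparison uses a separate analysis of covariance without parent terms. The change is worth making because it aligns a supporting test with its own hypothesis at little cost.

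**What to change.** In Section 10, Hypothesis 1b:

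1. Define the parent term as change from baseline to Week 20.
2. Include both arm × change and arm × baseline parent behavior, alongside arm, change, baseline parent behavior and baseline child score.
3. Name the arm × change coefficient as the Hypothesis 1b interaction test.
4. Keep arm × Week 20 level as a sensitivity analysis, labeled as addressing attained level.
5. As a clarification, center the parent measures, code arm as −1/2 and +1/2, and report the parent main effect as the average slope over both arms.

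Apply this to both parent measures and to the repeated secondary-outcome analyses, and settle it before unblinding.

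The cost is a few sentences, one degree of freedom, and lower power than the planned term if attained level is the true moderator. No new data are needed. The section should also acknowledge that the interaction test may well be underpowered at n = 50.

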In summary, the behavioral component of the proposed multi-modal treatment will be a PILI that targets improvements in spoken language and challenging behavior for 10- to 17-year-olds with FXS by increasing PVR within picture-book based storytelling episodes. Finally, parents/caregivers will be encouraged to use the targeted strategies in other everyday interactions with their child. The intervention will be delivered to parents/caregivers in their homes by way of VTC. Considerable preliminary work will need to be conducted, however, before combining it with lovastatin. Thus, we propose to spend the first 18 months of the project conducting two small-scale studies of PILI alone. The first phase (Phase 1) of the PILI study was designed to collect preliminary data, enrolled three mothers and their sons and will be completed by end of December 2014. NIH has requested that we continue to test the preliminary efficacy of the behavioral intervention using a small N group design study prior to implementing the phase of the intervention which includes the drug Thus, the second phase of the study (Phase 2) will be a group design (N=30) with randomized assignment to a Treatment Group or a Wait List Comparison Group. Participants in the Treatment Group receive the behavioral intervention and the Wait List Comparison Group receives treatment as usual. The final phase of the study (Phase3) will be a clinical trial (N=50) in which participants are randomly assigned to receive the behavioral intervention alone or in combination with Lovastatin.

5) Inclusion and Exclusion Criteria

Subjects will be screened initially through a pre-screening form either over the phone or in person at the MIND Institute. If the subject is eligible based on the responses to the pre-screening form they will be given the option of scheduling a screening visit to complete screening assessments and confirm if language level and overall functioning are adequate to participate in the trial.

Inclusion Criteria:

- 1. Documentation of a full mutation with absence or deficient FMRP levels.
- 2. Males and females ages 10 through 17 years (Consent Forms A and B). Note:

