We propose to conduct a study of the efficacy of the adapted PILI program during the first 18 months of the IDDRC funding period. We expect to enroll up to 30 participants and employ a series of single-case designs and PILI vs. treatment-asusual group comparison design, with the latter group receiving no intervention other than what they are already receiving in the community and will participate only in pre- and post-treatment assessments. The treatment-as-usual participants will have the opportunity to go into the multimodal study, or clinical trial portion of the project, which will serve to maintain the participant's commitment and participation in the absence of treatment. Note that there are many reasons to believe that the adapted PILI program will be efficacious. These include evidence from other languagedisordered populations of the utility of narrative as a good context for intervention for this age group and also evidence of the importance of parental verbal responsiveness (as embodied in PILI) to language development throughout childhood and into adolescence for individuals with FXS from longitudinal observational studies. Following the PILI only component, we will open enrollment into the clinical trial utilizing consent form B, and begin randomizing participants to lovastatin or placebo while receiving PILI.

In addition to the above studies, a separate study (ICF D) examining the feasibility of implementing PILI in a younger population of boys with FXS (ages 5- to 8-years of age) and their biological mothers will be conducted. We expect to recruit approximately 3 children whose participation will last approximately 3-6 months. The study implemented for this younger age group will follow similar procedures as described for the older children in consent form A, with the exception that the study materials will be adapted for children who are verbal but who are at the beginning stages of language development. Participation in this study will not require any visits to the MIND Institute; all information will be gathered through questionnaires and interactions via SKYPE.

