Half of the participants will receive the Parent-Implemented Language Intervention (PILI) under consent form A, the remaining half of participants will have the option to participate in the clinical trial portion of the study under consent form B, at which point they will be guaranteed to receive the PILI intervention.

All participants will receive the Parent-Implemented Language Intervention (PILI) under the clinical trial portion of the study, consent form B. In addition to PILI, half of the patients will be randomized to take lovastatin and may experience a beneficial response to lovastatin including heightened response to PILI with language improvements and reduction of problematic behaviors of FXS including ADHD,

aggression, and anxiety. All participants under consent form B will also benefit by receiving physical exams, cognitive assessments, and blood tests.

18) Vulnerable Populations

The patient population to be studied is developmentally disabled children with fragile x syndrome. We have done research with developmentally disabled and cognitively impaired individuals of all ages for many years. The consent process for individuals without the cognitive ability to consent will be completed by the parent, caregiver, or legally authorized representative (LAR), and no procedures will be done with any subjects without consent of either subject or parent/caregiver/LAR.

19) Sharing of Results with Subjects

At the conclusion of the study, the possible medical benefit from the study will be reviewed with the subject and his or her parent/guardian. Any laboratory work considered standard of care will be available for patients at their request. Psychological assessment scores may be communicated to the subjects if it does not impact future testing. If a subject has to be unblinded for emergency purposes then the subject will be notified by the principal investigator or study physician. Unblinding will be conducted in accordance with the MIND Institute's SOP# 500-014: Study Subject Unblinding Process. The results of the study may also be published or presented at scientific meetings including peer reviewed scientific journals that will be made publicly available through PubMed Central. In addition, after publication the results will be posted on the MIND Institute website under clinical trials

20) Setting

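### Hypothesis 1b reads two regression coefficients as a PILI effect and a combination effect, but every Phase 3 child receives PILI, so the trial identifies neither

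*Combined protocol and SAP*

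**What the plan says.** Section 3 (Objectives) words the first part of Hypothesis 1b as an association between parents' uptake of the taught strategies and child improvement. It then adds that this holds "especially in the lovastatin-treated group, thereby demonstrating benefit of the combined intervention".

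Section 10 (Study Endpoints, Aim 1, Hypothesis 1b) sets out the model: the child's 20-week outcome on treatment, parent behavior and their product, adjusted for baseline parent and child values, with parent confounders also evaluated. It gives a reading rule: the "main effect of the parent behavior will test the contribution of PILI, whereas the interaction term will test the value of the combined treatment". The analyses are run separately for two parent measures and repeated for the secondary outcomes. The last paragraph of Section 10 says that synergy between drug and language intervention is expected.

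The design is stated consistently:

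- Section 3: "Children will be randomized to drug or placebo in a double-blind design with all participating in the PILI".
- Section 4 (Background, Phase 3): "participants are randomly assigned to receive the behavioral intervention alone or in combination with Lovastatin".
- Section 11 (Procedures Involved): the trial will "begin randomizing participants to lovastatin or placebo while receiving PILI".
- Section 17 (Potential Benefits): "All participants will receive the Parent-Implemented Language Intervention (PILI) under the clinical trial portion of the study, consent form B".

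PILI against no PILI is randomized only in Phase 2 (N=30, no study drug). Section 4 describes "randomized assignment to a Treatment Group or a Wait List Comparison Group", and Section 11 a "PILI vs. treatment-asusual group comparison design".

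**The concern.** A treatment that everyone receives has no comparison group, so its effect cannot be read from differences among the people who received it. Families who take up the strategies more fully may differ in ways that also affect the child's language. Influence can also run from child to parent. Section 4 itself says that tantrums or refusal can make responsive interaction impossible. Among the parent variables listed in Section 11 (a) (Parent-Child Assessment Measures), expansions most clearly need a child utterance to respond to. If lovastatin changes the child, parent scores may follow.

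Under the plan's rule, a significant parent slope would be reported as the contribution of PILI, and a significant interaction as the value of combining the treatments. Either can occur with no causal parent effect. Because the plan already expects synergy, a significant interaction would probably be taken as confirmation.

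**Working it through.** The plan states no figure for Hypothesis 1b, so there is none to reproduce. Its 80% power statement concerns the primary comparison.

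**Step 1: what the design identifies.** Let μ be the mean outcome with neither treatment, π the PILI effect, δ the drug effect without PILI, and γ the synergy.

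| | No PILI | PILI |
|---|---|---|
| No lovastatin | μ | μ + π |
| Lovastatin | μ + δ | μ + π + δ + γ |

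Phase 3 fills only the PILI column. Its single randomized contrast is (μ + π + δ + γ) − (μ + π) = δ + γ, the effect of adding lovastatin to PILI. With PILI = 1 for all 50 children, the PILI column of the design matrix [1, drug, PILI, drug × PILI] equals the intercept and the product column equals the drug column. The rank is 2 of 4, so π is not estimable and γ cannot be separated from δ. Sample size plays no part.

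Phase 2 supplies the top row, and so π. No phase supplies lovastatin without PILI, so γ stays unidentified even with all phases together.

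**Step 2: what the two coefficients measure.** The parent term is the adjusted association between parent behavior and child outcome among families who all had PILI. The interaction is the difference in that association between arms. A PILI benefit equal for every child goes into the intercept, and an equal extra gain in the lovastatin arm goes into the treatment term. Neither reaches the coefficient that the plan assigns to it. A simulation (2,000 trials, 25 per arm, outcome SD about √(0.6² + 0.7²) = 0.92) agrees: a uniform PILI benefit of 1.0 left the parent term significant in 4.6% of trials, and a uniform gain of 0.6 in the lovastatin arm left the interaction at 5.0%.

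**Step 3: illustration of the opposite failure.** All correlations here are assumed. N = 50, 25 per arm, no treatment effect and no effect of parent on child. Outcome: y = 0.6·y₀ + 0.8·u. Parent behavior: p = 0.5·p₀ + √0.75·(g·u + √(1 − g²)·e). Here g is the residual parent-child correlation. The fit is least squares of y on treatment (−0.5/+0.5), p, their product, y₀ and p₀, which leaves 50 − 6 = 44 degrees of freedom, tested two-sided at 0.05. There are 20,000 trials per row, with Monte Carlo standard error at most 0.0035.

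| g, placebo | g, lovastatin | Parent term | Interaction | Both |
|---|---|---|---|---|
| 0 | 0 | 5.1% | 5.0% | 0.4% |
| 0.1 | 0.1 | 10.0% | 5.0% | 0.7% |
| 0.2 | 0.2 | 26.8% | 5.0% | 1.6% |
| 0.3 | 0.3 | 52.9% | 5.1% | 2.9% |
| 0 | 0.2 | 10.2% | 8.8% | 1.2% |
| 0 | 0.3 | 17.1% | 13.9% | 2.7% |
| 0 | 0.5 | 40.2% | 31.5% | 12.4% |

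The interaction stays near 5% when the correlation is the same in both arms and rises when it differs. As tests of no association, the rejections where g is not zero are correct. They mislead only under the labels in Section 10.

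**The case against.** The strongest reply is that this is wording, not analysis. Section 3 uses the language of association and Section 10 speaks of testing relationships. PILI is meant to work by raising parental responsiveness, so its contribution could be read as the contribution of strategy uptake, an ordinary process analysis. PILI efficacy is assigned to Phase 2. Hypothesis 1a does identify the gain from adding lovastatin to PILI, which is one natural sense of a combined treatment's value.

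Much of this stands: the model can be kept. But Section 10 says what each coefficient tests, and the gain under Hypothesis 1a is the treatment contrast, not the interaction. Baseline adjustment, confounder evaluation and blinded language coding reduce bias; they cannot supply the missing comparison.

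A reader might infer more than the documents support:

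- *That parent and child are certainly measured at the same time.* Section 10 gives no time for the parent measure. Section 11 (a) makes the post-treatment value most likely, but also describes weekly book-sharing sessions for data collection.
- *That the parent scores mostly depend on child speech.* Of the listed variables, expansions clearly do. Story-related talking, open-ended questions and intonation prompts need not.
- *That parent-completed ABC ratings distort the interaction.* The drug is double-blind, which limits reporting differences between arms.
- *That the simulated rates are the plan's false-positive rates.* They depend wholly on assumed correlations.
- *That unstated treatment coding is part of the error.* Coding affects what the parent term means: at g = 0.3 in both arms it is significant in 34% of trials with 0/1 coding, against 52% to 53% with −0.5/+0.5. Neither coding makes it a PILI effect.

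**Conclusion.** The stated reading rule is wrong and should be changed. Phase 3 identifies the effect of adding lovastatin to PILI. It identifies neither the effect of PILI nor synergy, and no phase identifies synergy. This follows from the allocation alone and needs no assumed figure. How often the labels would mislead is unknown, because the documents give no parent-child correlation.

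The damage is limited to Hypothesis 1b, which is not primary. A reader might conclude that the regression is invalid or that the trial's main result is compromised. The documents support neither: the regression is a sound test of association, and the primary analysis of covariance rests on the randomization.

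**What to change.** 1. In Section 3, delete the closing clause of Hypothesis 1b, from the word 'thereby' onward.

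2. In Section 10, replace the sentence that interprets the coefficients with the following, which keeps the link between each term and the hypothesis:

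   *The parent-behavior term (average slope across arms) tests whether parents' use of the strategies that PILI targets is associated with child outcome, and the interaction tests whether that association differs between lovastatin and placebo. Neither is a causal effect of PILI or of combining PILI with lovastatin. The randomized comparison estimates the effect of adding lovastatin to PILI (Hypothesis 1a); PILI versus no PILI is addressed by the randomized Phase 2 comparison.*

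3. In the last paragraph of Section 10, mark the synergy sentence as an expectation that no phase tests.

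Optionally, state that treatment is coded −0.5/+0.5, so that the parent term is the average slope. This clarifies the term but does not cure the mislabeling.

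The cost is editing only: no new data, visits or analyses. The downside is a weaker stated claim for a non-primary hypothesis.
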